#### **4.3.2. Secondary outcomes**

The secondary outcome for the study will be:

- 1) The (annualized) rate of exacerbations in patients controlled and uncontrolled at baseline
- 2) Time to the first composite event in patients controlled and uncontrolled at baseline
- 3) Time to the first exacerbations in patients controlled and uncontrolled at baseline
- 4) Comparison of CAT and CCQ as tools to identify impact and stability in COPD (i.e. a comparison of their scores' alignment with other relevant scores over the 24-month follow up period).
- 5) Distribution of control level across in those receiving guideline vs non-guideline recommended therapy (i.e. stratification of control across different treatment groups)
- 6) Demographic and clinical characteristics associated with poor control of COPD (i.e. comparison of control status across different demographic groups).

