#### **4.5. SAMPLE SIZE CALCULATION**

Based on a previous pilot study in Spain, approximately 55% of patients with COPD are controlled based on the proposed criteria. The sample size has to be calculated in order to have enough sample of both subgroups (controlled/non controlled) in both levels of severity (mild to moderate and severe to very severe) that will allow to identify differences in outcomes (main outcome: difference in annualised rate of composite outcome). Since there is not previous information about the frequency of the composite outcome, we have performed a conservative approach using the expected frequency of exacerbations in the sample calculation. According to results from ECLIPSE Study, annualised rate of exacerbations in COPD patients in entire sample was 1.2 per person (15). We hypothesize that, in controlled COPD patients, this annual rate can be 40% lower (0.72 per person). Accepting an alpha risk of 5% and a beta risk of 10% in a two-sided test, a total of 285 COPD patients will be necessary to find this annualised incidence ratio difference as statistically significant. It is expected that two thirds of controlled patients have mild to moderate COPD and one third of these have severe to very severe COPD. With an expected drop-out rate of 15%, a total of 328 patients will be enrolled in the study. Sample size has been calculated with !NI2IS macro (SPSS V20).

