### ***9.3.3. Analysis of primary and secondary outcomes***

Descriptive data are reported as means (standard deviations (SD)) or percentages, as appropriate. Comparisons between groups for descriptive summaries will be performed with the use of analysis of variance. The incidence of the composite endpoint (Mortality, hospitalisations and serious COPD morbidity) will be summarized as a per-person per-year rate.

Differences in the composite endpoint between groups (controlled and uncontrolled COPD patients) will be analyzed with the use of a nonparametric U-Mann Whitney test. In the initial exploration of data, composite endpoint will be analyzed as a qualitative variable (presence or not presence of death, hospitalisations or serious COPD morbidity) during year 1, with the use of logistic regression.

Multinomial logistic regression will be performed with the frequency of exacerbations during year 1 classified as none, one, or two or more to more fully characterize the associations between selected baseline factors and composite endpoint frequency.

Frequent exacerbations as two or more exacerbations in a year will be defined for the analysis.

A final multivariate logistic regression analysis will be used to calculate Odds ratios (OR) and their 95% confidence intervals (95%CI) for frequent exacerbations that will be included in the model as dependent variable. A previous analysis of potential confounding factors will be carried. The interaction was analyzed using the likelihood ratio test. Receiver operating characteristic (ROC) curves will be constructed derived from the final model to determine its capacity to predict endpoint. The Hosmer-Lemeshow goodness-of-fit test will be performed to assess the overall fit of the model (*Hosmer DW, Lemeshow S: Applied Logistic Regression, ed 1. New York, John Wiley and Sons Inc., 1989*).

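### The final adjusted exacerbation model is a logistic regression on two or more events in a year, although the related outcome and the sample size are annualised rates

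*Protocol*

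**What the plan says.** Section 4.3.2 lists as its first secondary outcome "The (annualized) rate of exacerbations in patients controlled and uncontrolled at baseline". Section 4.5 sizes the study on the same scale. It takes from an earlier cohort that the "annualised rate of exacerbations in COPD patients in entire sample was 1.2 per person" and supposes that in controlled patients "this annual rate can be 40% lower (0.72 per person", with 5% two-sided alpha and 90% power.

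Section 9.3.3 then names two regressions for exacerbations, and both work on a categorised count:

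- "Multinomial logistic regression will be performed with the frequency of exacerbations during year 1 classified as none, one, or two or more".
- A final multivariable logistic regression for frequent exacerbators, for which "Frequent exacerbations as two or more exacerbations in a year will be defined for the analysis". Odds ratios, ROC curves and a Hosmer-Lemeshow test follow from this model.

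The ANCOVA in section 9.3.4 covers EQ5, CCQ, lung function and BODE, not exacerbations. Control status is assigned at Visit 0, month 3 (section 4.4.2), and Table 4 places the later visits at months 9, 15 and 21.

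**The concern.** The groups are not randomised, so the confounder-adjusted result carries much of the weight of any claim that control predicts fewer exacerbations. The model fixed as final does not estimate the rate contrast declared as an outcome. It estimates the odds of crossing a threshold, treating 0 and 1 events as the same and 2 and 6 as the same.

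If the year is the first year, events in the last 6 of the 18 months after classification are not used. A patient who leaves before month 12 with 0 or 1 events then has no natural value on the outcome. Section 4.5 expects 15% drop-out, and section 9.4 names no imputation method.

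At stake is a null adjusted result that could come from the choice of scale alone, and a rate outcome reported without an adjusted rate ratio.

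**Working it through.** **Inputs from the protocol.** Rates 1.2 and 0.72 per person-year; 5% two-sided alpha; 90% power; "approximately 55% of patients with COPD are controlled based on the proposed criteria"; 285 evaluable, 15% drop-out, 328 enrolled (all section 4.5). Follow-up from Visit 0 to Visit 3 is 21 − 3 = 18 months.

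**Assumption.** Counts are Poisson (k = 0) or gamma-Poisson with dispersion k. The protocol gives no k, so a range is shown.

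**The plan's own figure.** 285 is roughly reproduced by comparing the proportions with at least one event in a year. These are 1 − exp(−1.2) = 0.699 and 1 − exp(−0.72) = 0.513, which need about 288 in total at 1:1 and 291 at 55/45. An incidence-density formula with one year of follow-up gives 280. A plain Poisson rate comparison over one year needs only 176 to 181. Enrolment is 285 × 1.15 = 328. The calculation below uses 328 × 0.85 = 279 evaluable patients: 0.55 × 279 = 153 controlled and 126 uncontrolled.

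**Count model.** The log rate ratio is ln(0.72/1.2) = −0.511. Over t years, its variance is (1/(1.2t) + k)/126 + (1/(0.72t) + k)/153. Power is Φ(0.511/SE − 1.96). For k = 0, SE is 0.125 at 12 months and 0.102 at 18 months, which gives 98.3% and 99.9%.

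**Threshold model, two or more events in 12 months.** For k = 0:

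- P(≥2) = 1 − exp(−1.2)(1 + 1.2) = 0.337 in uncontrolled patients, and 1 − exp(−0.72)(1 + 0.72) = 0.163 in controlled patients.
- The log odds ratio is 0.963 in size. Its SE is √[1/(126 × 0.337 × 0.663) + 1/(153 × 0.163 × 0.837)] = 0.289.
- The ratio is 3.33, and power is Φ(3.33 − 1.96) = 91.5%.

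| k | Logistic, ≥2 in 12 months | Count, 12 months | Count, 18 months | Loss from the cut alone | Total loss |
|---|---|---|---|---|---|
| 0 | 91.5% | 98.3% | 99.9% | 7 | 8 |
| 0.25 | 85.4% | 95.7% | 99.0% | 10 | 14 |
| 0.5 | 79.0% | 92.1% | 97.0% | 13 | 18 |
| 1.0 | 66.7% | 83.7% | 89.9% | 17 | 23 |

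Losses are in percentage points. All tests are unadjusted and assume complete follow-up for the 279.

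**Other reading of 1.2.** Section 4.5 describes 1.2 as the rate in the entire sample. With 55% of patients at 0.72, the uncontrolled rate would be (1.2 − 0.55 × 0.72)/0.45 = 1.79. The threshold model then has 96% power or more, and the total loss is about 0 points for k up to 0.5, 1 point at k = 1.0 and 4 points at k = 1.5.

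**Share of follow-up unused if the year is year 1.** 6/18 = 33%, counted from Visit 0.

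**The case against.** The case for leaving the plan alone has real force.

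- **Purpose.** Section 9.3.3 derives ROC curves from the final model to judge prediction, and section 1.1 gives predicting outcomes as part of what is to be validated. A binary frequent-exacerbator outcome suits that task, and a negative binomial model gives no direct ROC output. This stands. It is a reason to keep the logistic model, not a reason to leave the rate outcome without an adjusted rate analysis.
- **Absence.** An adjusted rate model could sit in a statistical analysis plan that is not shown. But section 9.3.3 does more than stay silent: it fixes a final model on another scale than the declared outcome.
- **Other analyses.** The multinomial model does separate 0 from 1 event, and it may be adjusted too. Time to first exacerbation is a separate secondary outcome that can use early leavers. Neither gives an adjusted rate ratio.

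Stronger readings are tempting, but the document does not support them:

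- **A power loss of 14 to 23 points follows from the plan's rates.** It does not. Those rates alone give about 8 points under Poisson; the rest needs an assumed dispersion.
- **The final model is restricted to year 1.** Year 1 is written for the exploratory composite model and for the multinomial model. The final-model sentences say only that the events fall within a year.
- **The primary analysis loses power.** It does not. The composite is compared by a Mann-Whitney test, which is neither cut at two nor limited to one year.

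**Conclusion.** The point holds as a mismatch of scale that should be corrected. The first secondary outcome and the sample-size basis are rates, while the model that section 9.3.3 fixes as final yields an odds ratio for a threshold.

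The size depends on two things the protocol does not settle: the dispersion of the counts, and whether 1.2 is the comparator rate or the whole-sample rate. At 1.2 against 0.72, the loss runs from about 8 points with no overdispersion to about 23 points at an assumed dispersion of 1.0. The cut alone accounts for about 7 to 17 of those points, and that part does not depend on discarding later months. With an uncontrolled rate near 1.79, the loss is about 0 to 4 points, and the benefit of a count model is mainly precision and agreement with the stated outcome. The calculation is unadjusted, so it indicates the loss in the adjusted model but does not measure it.

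**What to change.** In section 9.3.3, add a negative binomial regression of the number of exacerbations from Visit 0 to Visit 3 on control status, with log person-time as offset and the same confounders as the logistic model. Report the adjusted rate ratio with its 95% confidence interval as the adjusted analysis of the first secondary outcome.

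Keep the logistic model on two or more events in a year, with its ROC and Hosmer-Lemeshow output, and the multinomial model, for prediction and description of frequent exacerbators. State which 12 months the logistic model covers.

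The cost is a few lines of text and one more model in SAS 9.3, which section 9.3.4 already names. No new data or patients are needed. The small downside is that the exacerbation contrast will be reported as a rate ratio beside an odds ratio. The offset lets early leavers contribute the time they were observed, but it does not by itself remove bias if drop-out is related to exacerbations.

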## CLINICAL STUDY PROTOCOL SUMMARY

**Title of Study:** Validation of the Concept of COPD Control In Clinical Practice

**Protocol version:** 1.0

**Study Number:** REG-RES1503

**Chief Investigator:** [name]

**Clinical Research Organisation:** Respiratory Effectiveness Group

**Part study funder:** REG and Novartis

**Name of Active Ingredients:** NA

**Name of Investigational Product:** NA

**Phase of Clinical Development:** 4

**Number of Investigational Centres Planned:** approximately 10 Centres

**Country of the study:** International – Spain, France, UK, Ireland, Canada

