### Stability

Clinical stability over time is defined as a composite of the following over a 3-month evaluation period:

1. Absence of exacerbation (including the inherent phase of recovery from the exacerbation), AND
2. Absence of significant clinical worsening\* during a period of time, that is, that stability includes the absence of significant clinical changes and/or the presence of improvement (positive changes).

\*The CAT and CCQ have demonstrated potential utility in evaluate clinical changes over time (4,5). Clinically significant deterioration has been described as being associated with a change of ≥2 CAT points (6) and/or a change of ≥0.4 CCQ points (6).

Table 2. Definition of COPD stability by COPD Severity Category

Clinical stability over time (3-month evaluation period)		Mild to moderate severity (BODE/Ex ≤ 4 points)		Severe/very severe COPD (BODE/Ex > 5 points)	
		Stable	Unstable	Stable	Unstable
No Exacerbations	Exacerbations	None	≥1	None	≥1
AND					
No Clinical Worsening	Changes in the CAT	<2	≥2	<2	≥2
	AND/OR				
	Changes in the CCQ	< 0.4	≥ 0.4	≤ 20	>20

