### ***COPD history in the last 12 months (routine data and patient reported)***

A review of the routine data will also be performed to establish the number of COPD exacerbations (defined as acute course of antibiotics or oral steroids course for COPD or an emergency room attendance or hospitalisation for COPD) recorded in the 12-month period prior to screening visit.

Patients will also be asked the number of times they have had a COPD exacerbation in the 12 months prior to screening visit to confirm events recorded in the routine data.

CAT (total score and individual component responses), EQ5-D and CCQ will be evaluated to enable change in these measures/scores to be evaluated at follow-up visits.

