## **5. PATIENT MANAGEMENT DURING THE CONDUCT OF THE STUDY**

In accordance with a pragmatic study design, patients will receive usual care by their own physician during the conduct of the study. The time between visits, 3-6 months, is in accordance with usual clinical practice and the recommendations of guidelines for regular follow-up of moderate to severe COPD patients.

Other than attending the required number of clinical visits (baseline, and 4 follow-up visits) patients will not be contacted by the research team in relation to this study.

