### 8.1. Definition of Adverse Events

All types of Adverse Events are defined in Table 8, below.

Worsening of the disease during the study will be recorded as an Adverse Event only if the presentation and/or outcome is more severe than would normally be expected from the normal course of the disease in a particular patient.

An exacerbation of COPD is defined as worsening COPD requiring the use of systemic corticosteroids, antibiotics and/or emergency room visit or hospitalisation.

An COPD exacerbation will not be considered an Adverse Event unless it meets the criteria for a serious adverse event. COPD exacerbations that do not meet the criteria for reporting as a serious adverse event will be documented separately from Adverse Events.

Patients with a COPD exacerbation will not be discontinued from the study unless hospitalisation is required, the patient meets any of the stopping criteria in Section 8, or the Principal Investigator believes it is in the patient's best interest to be withdrawn from the study.

Table 8. Definition of adverse events

Adverse Event (AE)	An untoward medical occurrence which does not necessarily have a causal relationship to the IMP or comparator, such as: 
 
 intercurrent illnesses
 
 physical injuries
 
 events possibly related to concomitant medication
 
 significant worsening (change in nature, severity, or frequency) of the disease under study or other pre-existing conditions. (Note: A condition recorded as pre-existing that is intermittently symptomatic [eg, headache] and which occurs during the study should be recorded as an adverse event.)
 

Adverse Drug Reaction (ADR)	An untoward and unintended response to an IMP which has a reasonable causal relationship to the IMP
Unexpected ADR	An ADR whose nature, severity, specificity, or outcome is not consistent with the term or description used in the local/regional product labeling (e.g. Package Insert or Summary of Product Characteristics) should be considered unexpected.

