#### 9.3.1. *Baseline variables*

Baseline variables will include:

- Demographics and lifestyle:
  - Sex
  - Age

- Height, weight, BMI
- Occupation
- Impact:
  - Dysnea (mMRC score)
  - Sputum presence; sputum colour
  - Daily physical activity (minutes walked / day)
  - CAT
  - CCQ
  - Impact at time of assessment (High vs Low)
- Stability
  - Exacerbations in the last 3 months (patient-reported and based on clinical records)
  - Change in CAT and CCQ in the last 3 months (where available)
  - Stable (vs unstable) disease at time of assessment (Y/N)
- COPD Control Status:
  - Controlled
  - Poorly controlled
- Comorbidities
- COPD medications (and cost)
- Other concomitant medications (and cost)
- Lung function (FEV1, FVC, FEV1/FVC)
- BODE Index
- Smoking Status
  - History (pack years)
  - Current status

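### The primary Mann-Whitney test takes no account of centre or country, although treated exacerbations enter both the control definition and the primary endpoint

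*Protocol*

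**What the plan says.** **Setting.** The Protocol Summary plans "approximately 10 Centres" and gives the countries as "International – Spain, France, UK, Ireland, Canada". Section 5 adds that "patients will receive usual care by their own physician during the conduct of the study", so treatment thresholds are not standardised between sites.

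**Exacerbation.** The 12-month history review counts events "defined as acute course of antibiotics or oral steroids course for COPD or an emergency room attendance or hospitalisation for COPD". Section 8.1 has "worsening COPD requiring the use of systemic corticosteroids, antibiotics and/or emergency room visit or hospitalisation". Both definitions rest on treatment or service use.

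**Exposure.** The Stability definition requires "Absence of exacerbation (including the inherent phase of recovery from the exacerbation), AND" freedom from clinical worsening over a 3-month period. The definition of control at both severity levels repeats the requirement of no exacerbation.

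**Endpoint.** In section 4.3.1 the primary composite counts an exacerbation of COPD. It also counts unscheduled physician visits and emergency attendance for COPD, and all-cause hospitalisation or death.

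**Analysis.** Section 9.3.3 fixes the between-group comparison of the composite as a Mann-Whitney U test, with no strata and no covariates. For the later logistic model of frequent exacerbations it says only: "A previous analysis of potential confounding factors will be carried". The ANCOVA in section 9.3.4 likewise adjusts for confounders that it does not name. The list in section 9.3.1, opened by "Baseline variables will include", has neither centre nor country. The only centre mentioned in section 9 is the source of cost data.

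**The concern.** Nothing in this design balances control status across centres. A centre or health system that prescribes antibiotics or steroids at a lower threshold records more exacerbations in the 3-month window, so it classifies fewer patients as controlled. By the same habit it records more primary events during follow-up. Pooling such centres in one rank test can show better outcomes in controlled patients even if control carries no information among patients of the same centre. Local access to care acts in the same way through the unscheduled and emergency visits in the composite.

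This is a validation study whose hypothesis (section 2.1) is that control goes with better outcomes. A positive pooled result could not separate that hypothesis from differences in how centres treat. A Mann-Whitney test without strata has no place for centre, so for the primary comparison this is a stated method and not only a detail left to a statistical analysis plan.

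**Working it through.** **Inputs from the Protocol.** About 10 centres (Summary); 285 evaluable patients, 55% controlled and 1.2 exacerbations per person-year (section 4.5); a 3-month stability window; follow-up from visit 0 at 3 months to visit 3 at 21 months, so 21 - 3 = 18 months. Average centre size is 285/10 = 28.5.

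**Assumed, because the documents do not give it.** The SD of the log exacerbation rate between centres, taken as 0.2, 0.3 or 0.5. The 95% range of centre rates is exp(2 x 1.96 x SD): 2.2-fold, 3.2-fold and 7.1-fold.

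**Mechanism, by hand.** Take two equal centres, one SD above and one SD below the reference rate, with SD 0.5 and Poisson counts. Within each centre, control is unrelated to later events.

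- Rates: 1.2 x exp(0.5) = 1.98 and 1.2 x exp(-0.5) = 0.73 per year.
- No exacerbation in 3 months: exp(-0.25 x rate) = 0.61 and 0.83.
- Share with low impact, set so that 55% are controlled at rate 1.2: 0.55/exp(-0.30) = 0.74.
- Controlled: 0.74 x 0.61 = 0.45 and 0.74 x 0.83 = 0.62.
- Mean events in 1.5 years: 2.97 and 1.09.
- Pooled mean in controlled patients: (0.45 x 2.97 + 0.62 x 1.09)/(0.45 + 0.62) = 1.88.
- Pooled mean in uncontrolled patients: (0.55 x 2.97 + 0.38 x 1.09)/(0.55 + 0.38) = 2.20.
- Rate ratio: 1.88/2.20, about 0.86, although it is 1 within each centre.

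**False-positive rate, by simulation.** About 280 patients in 10 equal centres, 18 months of follow-up, window and follow-up counts linked only through the centre rate, two-sided 5% level. Frailty means gamma variation between patients of 0.7.

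| SD of log rate (assumed) | Planned test, frailty 0.7 | Spurious rate ratio, frailty 0.7 | Planned test, no frailty |
|---|---|---|---|
| 0.2 | 5-6% | 0.98 | 5.3% |
| 0.3 | 6% | 0.95 | 8.3% |
| 0.5 | 12-15% | 0.86-0.89 | 28% |

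With no between-centre variation and no frailty, the planned test rejects in 4.3%. The van Elteren test stratified by centre stays between about 4% and 5.5% in every setting. Ranges reflect repeated runs.

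**If the share with low impact also varies by centre** (logit SD 0.5, correlation of size 0.5 with the exacerbation rate, frailty 0.7), the rate at SD 0.5 depends on the sign. It is about 21-25% if centres with more exacerbations have fewer low-impact patients, and about 7% if they have more. The stratified test stays at about 5% in this setting too.

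**The case against.** **Centre handling is ordinary SAP content.** This holds for the logistic and ANCOVA models. A reader might infer that the Protocol excludes centre from every analysis. It does not: the confounders there are unnamed, and nothing confines them to the section 9.3.1 list. The objection fails for the primary test, which is fixed without strata.

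**The size is unknown and may be negligible.** This stands. At SD 0.2 the planned test is close to its nominal level, and with frailty it is little worse at 0.3. The spurious ratios of 0.98 and 0.95 are far from the planned 0.72/1.2 = 0.60. The larger error rates need about a 7-fold range of centre rates. At that SD the figure also moves between 12-15% and 28% according to how much patients vary within a centre.

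**The direction is not fixed.** A reader might infer that the bias always favours control. It does when only the exacerbation rate varies by centre. If low impact varies as well, the opposite sign nearly cancels it, and no passage says which sign applies.

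**Two further inferences are not supported.** One is that a confidence interval for the prevalence of control would be too narrow: the Protocol specifies no such interval. The other is that every between-group comparison should be made within centre. For the secondary objective on guideline-recommended prescribing, differences between centres in prescribing are part of the exposure.

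**Conclusion.** The point holds for the primary between-group test. In a non-randomised multicentre cohort, the Protocol fixes a test that cannot separate control from centre, and the same treatment-defined event sits in both the exposure and the endpoint. The mechanism follows from the documents. The size does not, and rests on an assumed between-centre SD: negligible at 0.2, small to moderate at 0.3, and material at 0.5, where false positives are about 12-15% with frailty 0.7, 28% without frailty, and 7-25% if low impact also varies by centre. These figures assume 10 equal centres and count exacerbations only. They show that the planned test is exposed to the problem. They do not show that its error will exceed 5% in this study. For the other outcome models, the narrower conclusion is that centre or country should be named.

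**What to change.** In section 9.3.3, stratify the primary rank test by centre, or by country where centres are small (van Elteren). Alternatively, use a rate model with a fixed or random centre effect and log follow-up time as offset. Name centre or country among the confounders in the logistic and ANCOVA models of outcome. Leave the guideline-prescribing objective outside this requirement.

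The cost is a few lines of text. Centre should be recoverable without new data, since patient numbers are assigned consecutively within each centre and the eCRF holds practice identifiers. Ten centres as fixed effects use 10 - 1 = 9 degrees of freedom. Sparse strata are the practical limit: if the analysis is also split by severity, as section 9.3 plans, 285/(10 x 2 x 2) is about 7 patients per cell on average. Country strata or a random centre effect would be the safer choice there.

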longitudinal concept that requires the absence of exacerbations and deterioration in the aforementioned variables or in CAT or CCQ scores. Hence, control is defined as a condition that has both low impact (adjusted for severity) and stability (14).

Having proposed the concept of control in COPD, it is now important to establish whether it has clinical validity and utility, specifically in terms of predicting outcomes and guiding on-going COPD management (and/or whether the measure may benefit from further refinement).

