### 2.2. Primary objectives

Following the publication of the Concept of COPD Control (6) and building on a retrospective pilot study designed to characterize evaluate the clinical implications of COPD control status within a UK primary care COPD population, the aim of this study is to validate the concept of control utilizing an international, multi-centre prospectively trial design.

The primary aims of the study will be to evaluate, in an international cohort of routine care / unselected COPD patients, the:

- 1) Levels of COPD control (vs poor COPD control), and
- 2) Clinical implications of control status.

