### 2.3. Secondary objectives

With a view to identifying opportunities to refine the tool to optimize its clinical utility and ability to guide treatment decisions to improve COPD outcomes (reduce disease burden and improve stability) and to identify patients in whom it may be best targeted (in terms of beneficially modifying outcomes and achieving cost efficiencies, a number of secondary objectives will also be evaluated. The secondary objectives of the study will aim to:

- 1) Compare the utility of the COPD Control (as defined) as a tool to identify COPD impact and stability with the CAT and CCQ;
- 2) Evaluate the role of “adequate” (i.e. guideline-recommended) treatment prescribing on COPD control.
- 3) Identify demographic and clinical characteristics associated with COPD control status

[figure not shown]

Table 4. Visit summary

Visit number	-1	0	1, 2 and 3
Time of Visit	Inclusion	Baseline 3 months	9, 15 and 21 months or discontinuation
Inclusion/Exclusion criteria	✓		
Information & Informed consent	✓		
Clinical assessment	✓	✓	✓
Assessment of exacerbations since last visit*	✓	✓	✓
Assessment of clinical status since last visit	✓	✓	✓
CAT/CCQ	✓		
Adverse events		✓	✓

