#### **9.3.4. Analysis of secondary outcomes**

Secondary outcomes (EQ5, CCQ, changes in lung function, BODE index) will be analyzed using analysis of covariance (ANCOVA), once assumptions for the convenience of this analysis are confirmed, with baseline values and potential confounding factors as covariates and study group as independent variable (Miller, G. A., & Chapman, J. P. 2001). After, Least square (LS) mean  $\pm$  standard error (SE) will be calculated for variables involving each outcome.

Baseline differences between study groups (controlled and uncontrolled COPD patients) will be performed using the Chi-square test (exact Fisher test with observed frequencies  $< 5$ ) for categorical variables whereas continuous variables were tested using *t* test (U-Mann Whitney test if the variables were not normally distributed). A stepwise multivariate logistic regression model to predict control in COPD patients will be performed. All variables explored in the univariate analyses will be considered in the multivariate model as covariates. A conservative significance threshold of 0.01 was used to determine the qualification of data for entry into or deletion from the model.

Finally, an analysis will be performed to evaluate the cost-utility of patients with controlled (as compared to poorly controlled) COPD using analysis of covariance. Data will be collected from the economic department of each collaborating center.

All tests were two-tailed, and significance was set at 5%. All analyses will be carried out using SPSS version 20, SAS version 9.3 and Microsoft Office EXCEL 2007.

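### The ROC curve of the final model for frequent exacerbations is read as predictive capacity in the cohort that built the model: taken as written, the AUC is optimistic and cannot show what control status itself predicts

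*Protocol*

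**What the plan says.** Protocol section 9.3.3 builds towards a single final multivariable logistic model. Its dependent variable is not the primary composite but a yes/no exacerbation outcome: "Frequent exacerbations as two or more exacerbations in a year will be defined for the analysis". Two data-based steps go with it: "A previous analysis of potential confounding factors will be carried" and "The interaction was analyzed using the likelihood ratio test". Predictive performance is then read as follows: "Receiver operating characteristic (ROC) curves will be constructed derived from the final model to determine its capacity to predict endpoint". A Hosmer-Lemeshow test is added for fit.

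The purpose is set elsewhere. Section 1.1 says "it is now important to establish whether it has clinical validity and utility, specifically in terms of predicting outcomes". Section 2.2 says "the aim of this study is to validate the concept of control". Section 2.3 lists as a secondary objective: "Compare the utility of the COPD Control (as defined) as a tool to identify COPD impact and stability with the CAT and CCQ".

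Section 9.3.3 names no second cohort, split sample, cross-validation or bootstrap. It does not say that control status is a term in the final model. It does not specify a ROC curve for control status alone, for the model without it, or for CAT and CCQ.

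**The concern.** There are two separate problems.

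**Optimism.** Coefficients are chosen to fit the patients at hand. A ROC curve drawn on those patients rewards the model for fitting their noise, and any covariate or interaction chosen on the same data adds to this. The direction of the bias is known; only its size is open. The Hosmer-Lemeshow test on the same patients does not detect it.

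**Wrong quantity.** A study meant to validate control needs to know how well control predicts, alone or on top of what is already measured. The AUC of a model with several covariates answers neither question. The baseline variables in section 9.3.1 include ingredients of control itself (dyspnoea, sputum, walking time, CAT, CCQ, recent exacerbations), so a respectable AUC could arise with control adding little.

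At stake is the interpretation: a good whole-model AUC could be taken as support for the control concept when part of it is overfitting and most of the rest comes from other variables.

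**Working it through.** The protocol gives no AUC, so there is no figure to reproduce. The check asks how large the bias could be on the protocol's own planning figures.

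**Inputs from section 4.5:** 55% controlled; 0.72 exacerbations per year if controlled; 1.2 as reference rate; 285 patients needed; 328 enrolled.

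**Assumptions not in the protocol:** 1.2 is used for the uncontrolled group; counts are negative binomial with dispersion k = 0.5 (0 to 1.0 as a range); there are 5 to 30 candidate covariates (section 9.3.1 lists roughly 20 to 30 baseline variables), three of them truly predictive; either all are kept or they are screened at univariate p < 0.10 with control status forced in.

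**Step 1, number of events.** With mean m and p = 1/(1 + km), P(0) = p^(1/k) and P(1) = (1/k)·P(0)·(1 − p). For k = 0.5:
- Controlled, m = 0.72: p = 0.7353, P(0) = 0.5407, P(1) = 0.2862, so P(≥2) = 0.173.
- Uncontrolled, m = 1.2: p = 0.625, P(0) = 0.3906, P(1) = 0.2930, so P(≥2) = 0.316.
- Overall: 0.55 × 0.173 + 0.45 × 0.316 = 0.238, about 24%.

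That is 285 × 0.238 ≈ 68 frequent exacerbators (66 to 69 for k from 1.0 to 0), or about 78 of 328 (76 to 79). With 20 to 30 candidates, 68/30 = 2.3 to 68/20 = 3.4 events per candidate.

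**Step 2, AUC of control status alone.** For a binary marker, AUC = 0.5 + (sensitivity − false-positive rate)/2.
- Share uncontrolled among frequent exacerbators: 0.45 × 0.316/0.238 ≈ 0.60.
- Share uncontrolled among the others: 0.45 × 0.684/0.762 ≈ 0.40.
- AUC ≈ 0.5 + 0.20/2 = 0.60. Over k from 1.0 to 0 it is about 0.59 to 0.62.

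**Step 3, optimism.** Logistic models were fitted to simulated cohorts of 285 (200 replicates per setting). The in-sample AUC was compared with the AUC of the same fitted model in 20,000 new patients.

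| Candidates | All kept | Screened | Rounded range over repeated runs |
|---|---|---|---|
| 5 | 0.04 | 0.03 | 0.03–0.04 |
| 10 | 0.06 | 0.05 | 0.05–0.07 |
| 20 | 0.11 | 0.07 | 0.07–0.12 |
| 30 | 0.16 | 0.08 | 0.08–0.16 |

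With 328 patients and all covariates kept, the values are similar: 0.06 for 10 and 0.11 for 20. If nothing predicts at all (true AUC 0.50), the in-sample AUC is still 0.59, 0.62, 0.67 and 0.70 for 5, 10, 20 and 30 covariates, and 0.55 to 0.62 after screening.

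**Step 4, what control contributes.** With 10 covariates, three predictive, all kept, the in-sample AUC is about 0.73 with control status and 0.70 without it. With 20 it is 0.763 against 0.738; with 30, 0.787 against 0.768. The difference is about 0.02 to 0.04 across settings, although control carries a true rate ratio of 0.72/1.2 = 0.6. Reading only the larger number of each pair says nothing about that difference.

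**The case against.** The strongest reply is that section 9.3.3 is silent on resampling and does not exclude it; the statistical analysis plan is not shown and could add a correction. This stands in part: the in-sample reading is inferred from the single cohort and from the curve being derived from the final model. But the section does fix a method and its interpretation, and followed as written it gives the biased figure.

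Second, no screening rule or candidate count is given for this model, and examining confounders may mean clinical judgement. This stands, and it limits the size: with a few prespecified covariates optimism is small. Overfitting does not need selection, however; the column with all covariates kept has none.

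Third, the section claims predictive capacity for the model, not for control, and control's effect appears elsewhere: the controlled-versus-uncontrolled comparison, the rates and times to event in section 4.3.2, and the odds ratio if control is in the model. True, but association is not discrimination, and sections 1.1 and 2.2 make prediction by control the subject of the validation.

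Three stronger readings are tempting and not supported:
- **That the primary result is compromised.** The ROC curve is not listed as an outcome in section 4.3, and neither the comparison of the composite between control groups nor the odds ratios depend on it.
- **That the final model is chosen stepwise at 0.01.** That rule belongs to another model in section 9.3.4: "A stepwise multivariate logistic regression model to predict control in COPD patients will be performed".
- **That the inflation can be put at one figure.** Without a covariate count, only a range is defensible.

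**Conclusion.** The point holds in direction on both counts, with the size left as a range. Read as written, the AUC is biased upward by about 0.03 to 0.16, depending mainly on whether there are 5 or 30 candidates and whether they are screened. This rests on 285 patients, the section 4.5 rates, 55% controlled, dispersion 0.5 and three truly predictive covariates.

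The firmer half is the second, because it follows from what the section fixes and not from its silence: a single whole-model AUC cannot show what control predicts, and the section does not place control in the model. On the planning rates, control alone reaches only about 0.59 to 0.62, so the distinction matters for the validation claim. It is a worthwhile correction to a supporting analysis, not a threat to the primary one.

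**What to change.** In section 9.3.3:

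1. State that control status is a term in the final model.
2. Report the AUC of control status alone, and the change in AUC when it is added to the covariate model, each with a 95% confidence interval.
3. Report the final model's AUC and calibration slope corrected for optimism by bootstrap, repeating any data-driven choice of covariates or interactions in every resample.

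No extra patients, visits or data are needed. The cost is a little more programming and a lower reported AUC.
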